Section 1.1 Table 1 Schedule of Events Section 6.1.2.2 Day 0 – On-site Study Vaccination Section 6.1.2.3 Day 28 – In- person/Home Health Care Follow-up Visit (-1 to + 7 Days) Section 1 Synopsis Exploratory Objectives and Corresponding Endpoints Section 3 Objectives and Endpoints Table 2 Section 9.2.4.4 Mucosal hACE2 Receptor Binding Inhibition Assay Subset 9.3.2.3 Analysis of Exploratory Immunogenicity Endpoints	Specify terminology: SARS-CoV-2 mucosal IgA-mediated hACE2 receptor binding inhibition and/or antibody responses in a mucosal IgA-mediated hACE2 receptor binding inhibition assay.	Clarify that the hACE2 receptor binding inhibition assay is a mucosal IgA-mediated assay.
Section 6.1.1.2 Unscheduled Study Visits Section 6.1.2.8.2 Unscheduled Visit due to Suspected COVID-19	must contact the site within 3 days of symptom onset. If possible, the participant should be brought in for an in-person visit to help gather vital signs and do any necessary work up inclusive of physical examinationOnly in situations where the participant cannot come in, should a telehealth visit be planned. must contact sites within 3 days of symptom onset for an unscheduled telehealth visit due to suspected COVID 19.	To clarify that whenever possible an on-site rather than a telehealth visit will be conducted for participants with suspected COVID-19 illness.
Section 7.4.1 Prohibited Therapies	Topical tacrolimus and ocular cyclosporine are permitted. Use of inhaled glucocorticoids is prohibited. Rabies immune globulin should be administered if medically indicated.	Reference to prohibited use of inhaled glucocorticoids was removed.

Abbreviations: COVID-19 = coronavirus disease 2019; hACE2 = human angiotensin-converting enzyme 2;

IgA = Immunoglobulin A; SARS-CoV-2 = severe acute respiratory syndrome coronavirus 2.

TABLE OF CONTENTS

	_
STATEMENT OF COMPLIANCE	
SPONSOR'S APPROVAL	3
INVESTIGATOR'S AGREEMENT	4
SUMMARY OF CHANGES	5
LIST OF TABLES	10
LIST OF FIGURES	10
LIST OF APPENDICES	10
LIST OF ABBREVIATIONS	11
1 SYNOPSIS	14
1.1 Schedule of Events	17
2 INTRODUCTION	21
2.1 Background	21

	Study 2019nCoV-314 Objectives and Endpoints Study Groups and Treatments Investigational Treatments Used in This Study Case Definitions of Probable and Confirmed Myocarditis, Pericarditis, and Myopericarditis Management of Probable or Confirmed Myocarditis, Pericarditis, and Myopericarditis Cases Potential Immune-Mediated Medical Conditions Adverse Events Representing Complications Specific to COVID-19 ¹ Modified FDA Toxicity Grading Scale for Clinical Abnormalities (Local and General Systemic Reactogenicity) FDA Toxicity Grading Scale for Clinical Abnormalities (Vital Signs)

LIST OF FIGURES

Figure 1:	Flow Diagram for Study 2019nCoV-314	
-----------	-------------------------------------	--

LIST OF APPENDICES

Appendix 1:	Listings of Adverse Events of Special Interest	75
Appendix 2:	Toxicity Grading Scale for Clinical Abnormalities (Local and General Systemic Reactogenicity and Vital Signs)	77
Appendix 3:	Assessment of COVID-19 Severity	79

LIST OF ABBREVIATIONS

Abbreviation	Definition	
24/7	24 hours 7 days a week	
2019nCoV	Novel coronavirus	
AE	Adverse event	
AESI	Adverse event of special interest	
AHA	American Heart Association	
ANCA	Anti-neutrophil cytoplasmic antibody	
AR	Adverse reaction	
BMI	Body mass index	
CDC	Centers for Disease Control	
CI	Confidence interval	
COVID-19	Coronavirus disease 2019	
CRO	Clinical research organization	
ECG	Electrocardiogram	
eCRF	Electronic case report form	
EDC	Electronic data capture	
eDiary	Electronic participant-reported outcome diary application	
ELISA	Enzyme-linked immunosorbent assay	
EOS	End of study	
ER	Emergency room	
EU	European Union	
FAS	Full Analysis Set	
FDA	Food and Drug Administration	
GCP	Good Clinical Practice	
GLP	Good Laboratory Practice	
GMC	Geometric mean concentration	
GMEU	Geometric mean ELISA unit	
GMFR	Geometric mean fold rise	
GMT	Geometric mean titer	
GMTR	Geometric mean titer ratio (between groups)	
GP	Glycoprotein	
hACE2	Human angiotensin-converting enzyme 2	
HBV	Hepatitis B virus	
HEENT	Head, eyes, ears, nose, and throat	
HIV	Human immunodeficiency virus	
HPV	Human papilloma virus	

Abbreviation	Definition
IB	Investigator's Brochure
ICF	Informed consent form
ICH	International Council for Harmonisation
ID ₅₀	Inhibitory dilution at a concentration of 50%
IEC	Independent Ethics Committee
IgA	Immunoglobulin A
IgG	Immunoglobulin G
IM	Intramuscular
IMP	Investigational medical product
IND	Investigational New Drug
IRB	Institutional Review Board
IWRS	Interactive Web Response System
LB	Lower bound
LBCI	Lower bound confidence interval
LLOQ	Lower Limit of Quantitation
MAAE	Medically attended adverse event
MedDRA	Medical Dictionary for Regulatory Activities
MERS	Middle East Respiratory Syndrome
МНС	Major histocompatibility complex
mRNA	Messenger ribonucleic acid
NAb	Neutralizing Antibody
NVX-CoV2373	Prototype vaccine with Matrix-M adjuvant
NVX-CoV2515	Omicron BA.1 subvariant vaccine with Matrix-M adjuvant
NVX-CoV2601	Omicron XBB.1.5 subvariant vaccine with Matrix-M adjuvant
OTC	Over-the-counter
PCR	Polymerase chain reaction
PIMMC	Potential immune-mediated medical conditions
РР	Per-Protocol
РТ	Preferred term
r	Recombinant
RNA	Ribonucleic acid
S	Spike (protein)
SAE	Serious adverse event
SAP	Statistical analysis plan
SAR	Suspected adverse reaction
SARS-CoV	Severe acute respiratory syndrome coronavirus

Abbreviation	Definition
SARS-CoV-2	Severe acute respiratory syndrome coronavirus 2
SARS-CoV-2 rS	Severe acute respiratory syndrome coronavirus 2 recombinant spike protein nanoparticle vaccine
SCR	Seroconversion rate
Sf9	Spodoptera frugiperda
SII	Serum Institute of India
SMC	Safety Monitoring Committee
SOC	System organ class
SOE	Schedule of Events
SOP	Standard operating procedure
Td	Tetanus diphtheria
Tdap/Dtap	Tetanus, diphtheria and pertussis
TEAE	Treatment-emergent adverse event
UK	United Kingdom
US	United States
VOC	Variants of concern
VRBPAC	Vaccines and Related Biological Products Advisory Committee
WHO	World Health Organization

1 SYNOPSIS

Study Title	A Phase 3, Randomized, Double-Blinded Study to Evaluate the Safety and Immunogenicity of Omicron Subvariant and Bivalent SARS-CoV-2 rS Vaccines in Adolescents Previously Vaccinated with mRNA COVID-19 Vaccines
Short Title	Phase 3 Adolescent Study for SARS-CoV-2 rS Variant Vaccines
Study Phase	3
Study Design	 This is a Phase 3, randomized, double-blinded study to evaluate the safety and immunogenicity of booster doses of Omicron subvariant severe acute respiratory syndrome coronavirus 2 (SARS-CoV-2) recombinant rS spike (S) protein nanoparticle vaccines (SARS-CoV-2 rS) adjuvanted with Matrix-MTM adjuvant (NVX-CoV2601 [Omicron XBB.1.5]) and bivalent (NVX-CoV2373 [prototype] + NVX-CoV2601) in previously vaccinated adolescent participants ≥ 12 to < 18 years of age. Approximately 400 adolescents who have received a regimen of ≥ 2 doses of the Moderna and/or Pfizer-BioNTech monovalent and/or bivalent COVID-19 vaccines ≥ 90 days previously will be randomized 1:1 to Group A or Group B: Group A: 1 dose of NVX-CoV2601 (1 on Day 0) Group B: 1 dose of bivalent NVX-CoV2373 + NVX-CoV2601 (1 on Day 0) All participants will remain on study for immunogenicity and safety data collection through Day 180.
Rationale	 Novavax, Inc., is developing recombinant vaccines adjuvanted with the saponin based Matrix-M adjuvant for the prevention of disease caused by SARS-CoV-2. Given the widespread circulation of Omicron subvariants, regulatory body discussions, and the associated decreased immunogenicity and efficacy of previously approved vaccines based on the prototype Wuhan strain, vaccines based on the Omicron subvariant XBB.1.5 (NVX-CoV2601) were developed and are being evaluated for safety and immunogenicity. The Omicron subvariant product in this study will also be used in combination with a prototype (Wuhan-Hu-1) NVX-CoV2373 in the form of a site-mixed bivalent vaccine to explore the safety and immunogenicity of vaccines containing antigen for both the ancestral (Wuhan) and XBB.1.5 subvariant strains of SARS-CoV-2. This study is designed to assess the safety and immunogenicity of the Novavax Omicron XBB.1.5 subvariant vaccine (NVX-CoV2601) alone or in combination with the prototype Novavax vaccine (NVX-CoV2373) as a bivalent product in adolescent participants ≥ 12 to < 18 years of age who previously received ≥ 2 doses of approved/authorized monovalent and/or bivalent mRNA vaccines. The safety profile of the booster dose will be assessed along with its ability to increase antibody titers against the Omicron XBB.1.5 subvariant. If favorable safety and immunogenicity profiles are observed following the booster dose of NVX-CoV2601 or the bivalent product, this would support the use of bivalent, variant based vaccines in adolescents in the global COVID-19 vaccination effort.
Target Population	Medically stable male and non-pregnant female adolescents ≥ 12 to < 18 years of age. All participants will have received a regimen of ≥ 2 doses of the Moderna and/or Pfizer-BioNTech COVID-19 monovalent and/or bivalent vaccines ≥ 90 days prior to study vaccination.

Number of	Approxim	ately 400 partic	ipants				
Participants	Group	Previous Vaccine	Novavax Vaccine Booster (antigen/adjuvant)	n			
	А	≥ 2 doses Moderna	NVX-CoV2601 (5 μg/50 μg)	200			
	В	and/or Pfizer- BioNTech	Bivalent NVX-CoV2373 + NVX-CoV2601 (5 μg/50 μg [total])	200			
Length of Participation	5 (e	ning and follow-up): days (7 months)				
Interventions	 with M conce admin Matrix 2. Protot prepar All in total a 	Matrix-M adjuv ntration of 10 μ istered in a 0.5 c-M adjuvant. ype/XBB.1.5 E red by combinin jections will be	g): Coformulated Omicron XBB.1.5 SARS-CoV ant: supplied as a solution for preparation for in ag antigen and 100 μ g adjuvant per mL. All inject mL injection volume at a dose of 5 μ g antigen v Bivalent Vaccine (5 μ g): A site-mixed bivalent v ng 0.25 mL of NVX-CoV2373 and 0.25 mL NV administered in a 0.5 mL injection volume at a prototype antigen + 2.5 μ g Omicron XBB.1.5 at want.	jection, at a ctions will be with 50 μg accine X-CoV2601. dose of 5 μg			
Primary Safety Objective and Endpoints	NVX-CoV Endpoints: Incide (AEs) Incide vaccin Incide study potent perica	 Objective: To assess the overall safety of 1 heterologous booster dose of NVX-CoV2601 and the bivalent vaccine (NVX-CoV2373 + NVX-CoV2601). Endpoints: Incidence, duration, and severity of solicited local and systemic adverse events (AEs) for 7 days following vaccination. Incidence, severity, and relationship of unsolicited AEs through 28 days after vaccination 					
Primary Immunogenicity Objective and Endpoints	Objective: NVX-CoV the Omicro • Neutra XBB.	XBB.1.5 strain, assessed at Day 28 following initial study vaccination.					
Secondary Objectives and Corresponding Endpoints	vaccine (N time. Endpoints: NAb (180).	VX-CoV2373 GMTs to the Or	e the NAb response induced by NVX-CoV2601 and the bivalen 373 + NVX-CoV2601) against the Omicron XBB.1.5 strain ove e Omicron XBB.1.5 strain at relevant time points (Days 0, 90, and elevant time points (Days 90, and 180) from baseline (Day 0).				

	Objective: To describe immunoglobulin G (IgG) antibody levels induced by
	NVX-CoV2601 and the bivalent vaccine (NVX-CoV2373 + NVX-CoV2601) against
	the Omicron XBB.1.5 strain over time.
	Endpoints:
	• IgG geometric mean ELISA (enzyme linked immunosorbent assay) units (GMEUs) to the Omicron XBB.1.5 S protein at relevant time points (Days 0, 28, 90, and 180). Derived/calculated endpoints based on these data will include GMFR.
Exploratory	Objective: To describe the NAb and IgG antibody responses induced by
Objectives and	NVX-CoV2601 and the bivalent vaccine (NVX-CoV2373 + NVX-CoV2601) against
Corresponding	the ancestral (Wuhan) strain over time.
Endpoints	Endpoints:
	• NAb titers and IgG GMEUs to the ancestral (Wuhan) strain at relevant time points (Days 0, 28, 90, and 180). Derived/calculated endpoints based on these data will include GMFR.
	Objective : To describe antibody responses in a human angiotensin converting enzyme-2 (hACE2) receptor binding inhibition assay induced by NVX-CoV2601 and the bivalent vaccine (NVX-CoV2373 + NVX-CoV2601) to the Omicron XBB.1.5 and ancestral (Wuhan) strains over time.
	Endpoints:
	 GMTs to the Omicron XBB.1.5 and ancestral (Wuhan) strains at relevant time points (Days 0, 28, 90, and 180). Derived/calculated endpoints based on these data will include GMFR.
	Objective: To describe antibody responses in a mucosal IgA-mediated hACE2 receptor binding inhibition assay induced by NVX-CoV2601 and the bivalent vaccine (NVX-CoV2373 + NVX-CoV2601) to the Omicron XBB.1.5 and ancestral (Wuhan) strains over time.
	Endpoints:
	• GMTs to the Omicron XBB.1.5 and ancestral (Wuhan) strains at relevant time points (Days 0 and 28). Derived/calculated endpoints based on these data will include GMFR.
	Objective: To utilize additional assays (current or to be developed) to better characterize the immune response for future vaccine development needs.
	Endpoint: Additional endpoints to evaluate immune responses may be developed based on the assays used.
	Objective: To characterize the severity of COVID-19 in participants who become infected during the course of the study.
	Endpoint: Detected case will be characterized as mild, moderate, or severe as assessed using the provided criteria.
Number of Sites	Up to 25 sites in the United States and Canada (Canadian sites contingent upon additional approval).
Study Duration	Estimated duration: Approximately 7 months
	1

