3 OBJECTIVES AND ENDPOINTS

The primary objectives in this study are to assess the overall safety of 1 heterologous booster dose of NVX-CoV2601 and the bivalent vaccine (NVX-CoV2373 + NVX-CoV2601) and to describe the NAb responses induced against the Omicron XBB.1.5 strain. An overview of the study objectives and endpoints is provided in Table 2.

Tier	Objectives	Endpoints
Primary Safety Objective and Endpoints	To assess the overall safety of 1 heterologous booster dose of NVX-CoV2601 and the bivalent vaccine (NVX-CoV2373 + NVX-CoV2601).	 Incidence, duration, and severity of solicited local and systemic AEs for 7 days following vaccination. Incidence, severity, and relationship of unsolicited AEs through 28 days after vaccination Incidence and severity of MAAEs attributed to study vaccine, AESIs (predefined list including PIMMCs, myocarditis and/or pericarditis, and complications specific to COVID-19), and SAEs through day 180 or EOS.

 Table 2:
 Study 2019nCoV-314 Objectives and Endpoints

Tier	Objectives	Endpoints
Primary Immunogenicity Objective and Endpoints	To describe the NAb response induced by NVX-CoV2601 and the bivalent vaccine (NVX-CoV2373 + NVX-CoV2601) against the Omicron XBB.1.5 strain.	 NAb GMTs to the Omicron XBB.1.5 strain, assessed at Day 28 following initial study vaccination. NAb geometric mean fold rise (GMFR) at Day 28 from baseline (Day 0).
Secondary Objectives	To describe the NAb response induced by NVX-CoV2601 and the bivalent vaccine (NVX-CoV2373 + NVX-CoV2601) against the Omicron XBB.1.5 strain over time.	 NAb GMTs to the Omicron XBB.1.5 strain at relevant time points (Days 0, 90, and 180). NAb GMFR at relevant time points (Days 90 and 180) from baseline (Day 0)
	To describe immunoglobulin G (IgG) antibody levels induced by NVX-CoV2601 and the bivalent vaccine (NVX-CoV2373 + NVX-CoV2601) against the Omicron XBB.1.5 strain over time.	• IgG GMEUs to the Omicron XBB.1.5 S protein at relevant time points (Days 0, 90, and 180). Derived/calculated endpoints based on these data will include GMFR.
Exploratory	To describe the NAb and IgG antibody responses induced by NVX-CoV2601 and the bivalent vaccine (NVX-CoV2373 + NVX-CoV2601) against the ancestral (Wuhan) strain over time.	 NAb titers and IgG GMEUs to the ancestral (Wuhan) strain at relevant time points (Days 0, 90, and 180). Derived/calculated endpoints based on these data will include GMFR.

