4.1.2 Study Design

This is a Phase 3, randomized, observer blinded study to evaluate the safety and immunogenicity of a booster dose of Omicron XBB.1.5 subvariant SARS-CoV-2 rS vaccines adjuvanted with Matrix-M adjuvant in previously vaccinated participants.

Approximately 400 adolescents who have received a regimen of ≥ 2 doses of the Moderna and/or Pfizer-BioNTech monovalent and/or bivalent COVID-19 vaccines ≥ 90 days previously will be enrolled and randomized 1:1 to Group A or Group B.

- Group A: 1 dose of NVX-CoV2601 (1 on Day 0)
- Group B: 1 dose of bivalent NVX-CoV2373 + NVX-CoV2601 (1 on Day 0)

Participants will remain on study for immunogenicity and safety data collection through Day 180. A tabular summary of the study design is provided below in Table 3, and a complete outline of study procedures is provided in Section 6.1.2.

Group	Previous Vaccine	Novavax Vaccine Booster (antigen/adjuvant)	n
Α	\geq 2 doses Moderna	NVX-CoV2601 (5 μg/50 μg)	200
В	and/or Pfizer-BioNTech	Bivalent NVX-CoV2373 + NVX-CoV2601 (5 μg/50 μg [total])	200

Table 3: Study Groups and Treatments

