7.2.3 Extent and Maintenance of Blinding

This is a double-blind study. To maintain the blind, predetermined unblinded study site personnel will manage vaccine logistics, preparation, and potentially administration according to the Pharmacy Manual so as to maintain the blind from the remainder of the study site personnel and participants. The unblinded study site personnel may administer study vaccine if qualified to do so but will not be involved in study related assessments or have participant contact for data collection after administration of study vaccine.

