8.1 Definitions

- Adverse event An AE is any untoward medical occurrence associated with the use of an intervention in humans whether or not it is considered intervention-related. Any abnormal laboratory test results or other safety assessments (eg, physical examination, vital signs measurements) that are clinically significant in the medical and scientific judgment of the investigator (ie, not related to progression of underlying disease) will be considered AEs. An exacerbation of a chronic or intermittent pre-existing condition, including either an increase in frequency and/or intensity, will be considered an AE.
- Serious adverse event (SAE) An event is considered "serious" if, in the view of either the Investigator or Sponsor, it results in any of the following outcomes:
 - Death
 - A life-threatening AE (an event is considered "life-threatening" if, in the view of either the investigator or Sponsor, its occurrence places the patient or participant at immediate risk of death. It does not include an AE or suspected adverse reaction (AR) that, had it occurred in a more severe form, might have caused death.)
 - Inpatient hospitalization or prolongation of existing hospitalization. In general, hospitalization signifies that the participant has been detained, usually involving an overnight stay, at the hospital or emergency ward for observation and/or treatment that would not have been appropriate in the physician's office or outpatient setting. Hospitalization for elective treatment of a pre-existing condition that did not worsen from baseline is not considered an SAE.

- A persistent or significant incapacity or substantial disruption of the ability to conduct normal life functions
- A congenital anomaly/birth defect
- Important medical events that may not result in death, be life-threatening, or require hospitalization may be considered serious when, based upon appropriate medical judgment, they may jeopardize the patient or participant and may require medical or surgical intervention to prevent one of the outcomes listed in this definition. Examples of such medical events include allergic bronchospasm requiring intensive treatment in an emergency room (ER) or at home, blood dyscrasias or convulsions that do not result in inpatient hospitalization, or the development of drug dependency or drug abuse.

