9.5 Planned Interim Analyses

A formal interim analysis will be carried out when the complete data is available to evaluate the primary endpoint. A set of secondary and exploratory endpoints will also be analyzed at this time, dependent on the availability of data. The database extract is expected to include immunogenicity data and safety data through Day 28. An independent statistics organization or the internal statistics team will perform the analysis and receive unblinded data at the time of analyses, following final determination of participant exclusions from analysis populations and database extract. At the time of Day 28 data extract with receipt of the randomization list, the Sponsor will be unblinded at the participant level to prepare for regulatory submissions.

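### The blinding level is stated two ways, and Section 9.5 unblinds the whole Sponsor at the Day 28 extract while one primary safety endpoint runs to Day 180 and the Sponsor still has a say in seriousness

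*Protocol*

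**What the plan says.** **Label.** The title and synopsis say double-blinded: "This is a Phase 3, randomized, double-blinded study to evaluate the safety and immunogenicity of booster doses". Section 7.2.3 agrees: "This is a double-blind study". Section 4.1.2 says "This is a Phase 3, randomized, observer blinded study to evaluate the safety and immunogenicity". The protocol defines neither term.

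**Site blind.** Under Section 7.2.3, "predetermined unblinded study site personnel will manage vaccine logistics, preparation, and potentially administration according to the Pharmacy Manual", the purpose being "so as to maintain the blind from the remainder of the study site personnel and participants". The same section bars these staff from study assessments and from later contact with participants for data collection. Section 7.2.4.1 keeps the site team blinded to the end of the study and tells participants their product only after that.

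**Sponsor blind.** Under Section 7.2.4.2, an emergency code break triggers an automatic notice to the Sponsor and the CRO clinical team that does not disclose the assignment. Section 9.5, however, provides that at the Day 28 extract "the Sponsor will be unblinded at the participant level to prepare for regulatory submissions". Section 7.2.4.1, on planned unblinding, does not mention this event.

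**Safety endpoints and classification.** Section 3 (Table 2) lists three primary safety endpoints: solicited AEs to 7 days, unsolicited AEs to 28 days, and related MAAEs, AESIs "and SAEs through day 180 or EOS". Section 8.1 makes an event serious if, "in the view of either the Investigator or Sponsor, it results in any of the following outcomes". Causality is documented by the investigator (Section 8.1).

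**The concern.** The label conflict on its own is close to clerical. The substantive issue is that Section 9.5, followed as written, gives every participant's code to the whole Sponsor while a primary safety endpoint is still accruing. Sponsor staff receive every SAE and AESI report within 24 hours (Section 8.3), and their view alone suffices to make an event serious. No passage keeps those staff blinded after the extract. The protocol does treat the Sponsor as blinded up to then, since it withholds even a single emergency code from it.

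Counts will be small. With about 200 participants per group, one event made serious, or pursued harder by query, with knowledge of the arm would be visible in the table. Section 4.1.3 says that sample size and duration were chosen to favour the collection of safety data, so these tables are a main product of the study.

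**Working it through.** **1. The labels.** Double-blind: title, synopsis, Section 7.2.3. Observer blinded: Section 4.1.2. All are current body text and must be reconciled.

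**2. Who is blinded, and until when.**

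| Party | Status | Section |
|---|---|---|
| Participants | Blinded to end of study | 7.2.4.1 |
| Site team other than preparers and injectors | Blinded to end of study, except emergencies | 7.2.3, 7.2.4 |
| Preparers, possibly injectors | Unblinded; barred from assessments | 7.2.3 |
| Sponsor | Codes withheld, then released at participant level at the Day 28 extract | 7.2.4.2, 9.5 |

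**3. Which endpoints are exposed.** The 7-day and 28-day endpoints have no follow-up left if the extract follows the last Day 28 visit. Only the third endpoint does.

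**4. The share of that endpoint's follow-up after unblinding.** Let accrual be uniform over A days and let the codes be released L days after the last participant reaches Day 28. The protocol states neither A nor L, so both are assumptions. A participant entering on accrual day a is then at study day A + 28 + L − a, with max(0, 180 − that day) of follow-up left. If nobody has yet finished, the average share is

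(180 − (28 + L + A/2)) / 180.

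- Ceiling (A = 0, L = 0): (180 − 28)/180 = 152/180 = 84.4%. This requires release on each participant's own Day 28.
- A = 19, L = 0: (180 − 37.5)/180 = 79.2%.
- A = 19, L = 90: (180 − 127.5)/180 = 29.2%.
- A = 60, L = 60: (180 − 118)/180 = 34.4%.

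Averages over participants, counting those already finished as zero:

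| A (days) | L = 0 | L = 30 | L = 60 | L = 90 |
|---|---|---|---|---|
| 0 | 84.4% | 67.8% | 51.1% | 34.4% |
| 19 | 79.2% | 62.5% | 45.8% | 29.2% |
| 60 | 67.8% | 51.1% | 34.4% | 17.8% |
| 120 | 51.1% | 34.4% | 19.6% | 8.9% |

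The value A = 19 takes the synopsis duration of about 7 months at face value: 7 × 30.4 ≈ 213 days, less 194 days of participation (Section 6.1.1), leaves 19. This is a rough reading, because Section 6.1.1 also describes the 194 days themselves as about 7 months.

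**5. Size of counts.** The Section 9.1 figures reproduce: 1 − 0.95^200 = 99.996% and 1 − 0.99^200 = 86.6%. At the same 1% incidence, 200 × 0.01 = 2 events are expected per group, so one reclassified event changes 2 to 3.

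**The case against.** The strongest reply is that the mechanism has little to act on.

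- The Section 8.1 rule only adds events: the Sponsor cannot remove an investigator's classification.
- Most seriousness criteria are factual outcomes such as death or hospitalisation.
- After Day 28 only related MAAEs, AESIs and SAEs are collected (Section 8.2.2), and all three already belong to the same endpoint. Upgrading a related MAAE mostly moves it between components.
- AESIs are already reported as if they were SAEs (Section 8.2.3.2), and suspected myocarditis or pericarditis goes to a Central Cardiac Adjudication Committee (Section 8).
- Safety analysis is wholly descriptive (Section 9.3.1), and Section 9.5 discloses the unblinding openly.
- Access controls may sit in the SMC Charter or the Safety Management Plan, which are not shown.

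Most of this stands and narrows the point. It does not remove it. The important-medical-event criterion calls for judgment, the AESI lists are expressly not exhaustive (Appendix 1), and COVID-19 cases recorded as AEs form another pool that could be upgraded. Section 9.5 itself states no restriction on who at the Sponsor sees the codes.

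Two stronger readings are tempting. A reader might infer that the Sponsor alone controls seriousness; Section 8.1 gives the blinded investigator the same power. A reader might also infer that unblinded injectors compromise outcome assessment; Section 7.2.3 bars them from it.

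**Conclusion.** The point holds in a limited form. The blinding level is stated inconsistently. Separately, Section 9.5 gives all codes to an unrestricted Sponsor that can still influence the classification of one primary safety endpoint. The exposure covers Sponsor-side seriousness and AESI judgments and safety queries after the extract, and nothing else.

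Its size is uncertain. The ceiling is 84% of follow-up; about 29% to 79% applies with 19-day accrual and a lag of 0 to 90 days; the share falls below 10% with 120-day accrual and a 90-day lag. These are shares of person-time, not of biased events, and they rest on assumed accrual and lag.

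A reader might conclude that a large part of the Day 180 safety data is not blinded. The documents do not support that: participants and site assessors, who report and collect the events, stay blinded throughout, and investigators assign causality. This is a worthwhile, inexpensive improvement, not a defect that undermines the safety results.

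**What to change.** 1. Use one blinding description in the title, the synopsis and Sections 4.1.2 and 7.2.3. It should say who is blinded and until when: participants and site assessors, preparers and injectors, Sponsor and CRO safety staff, and the analysis group. List the Day 28 Sponsor unblinding under Section 7.2.4.1.
2. In Section 9.5, release participant-level codes only to a named, firewalled analysis and submission group. Keep Sponsor and CRO staff who judge seriousness, causality or AESI status, or who query sites on safety events, blinded until the final database lock. Section 9.5 already allows an independent statistics organisation to run the interim, so this fits the existing plan.
3. Optionally, for events after the extract, show SAEs made serious by the Sponsor alone separately from those the investigator classified as serious.

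The cost is amendment wording, a code-access list and, if item 3 is adopted, one extra split in the SAE table. It needs no extra participants or visits and no delay to the Day 28 analysis. The downside is that submission and safety-review roles must be kept separate for the remaining follow-up.
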